## 10.12 Appendix 12: Suggested management guidelines for infusion reactions

Type of reaction	Sponsor recommendations for management

Acute – Mild eg, flushing, dizziness, headache, sweating, palpitations, nausea
	
 
• Stop infusion.
 
• Infuse 0.9% sodium chloride 500-1000mL/h IV.
 
• Administer antihistamine IV/IM.
 
• Administer paracetamol 1g orally.
 
• Monitor vital signs every 10 minutes until back to Baseline. In case all infusion reaction signs and symptoms have resolved and investigator considers infusion restart clinically appropriate, the infusion can be restarted; the [REDACTED]
 

Acute – Moderate eg, flushing, chest tightness, dyspnea, hypo/hypertension (change >20mmHg in systolic blood pressure), raised temperature, palpitations, urticaria
	
 
• Stop infusion.
 
• Infuse 0.9% sodium chloride 500-1000mL/h IV.
 
• Administer antihistamine IV/IM.
 
• Administer paracetamol 1g orally.
 
• Monitor vital signs every 5 minutes until back to Baseline.
 

Acute – Severe eg, hypo/hypertension (change >40mmHg in systolic blood pressure), raised temperature with rigors, chest tightness, dyspnea with wheezing, stridor
	
 
• Stop infusion.
 
• Alert crash team.
 
• Maintain airway, ensure oxygen is available.
 
• If wheezing, give epinephrine 0.5mg IM (0.5mL 1:1000 epinephrine).
 
• Administer antihistamine IV/IM.
 
• Administer corticosteroids IV.
 
• Monitor vital signs every 2 minutes until back to Baseline.
 

IM=intramuscularly; IV=intravenous; MP>manual push

---

## 10.13 Appendix 13: Management of anaphylaxis

Anaphylaxis is highly likely when any of the following 3 criteria is fulfilled (Sampson et al, 2006):

1. Acute onset of an illness (minutes to several hours) with involvement of the skin, mucosal tissue, or both (eg, generalized hives, pruritus or flushing, swollen lips-tongue-uvula)

AND AT LEAST 1 OF THE FOLLOWING

- Respiratory compromise (eg, dyspnea, wheeze-bronchospasm, stridor, reduced peak expiratory flow, hypoxemia)
  - Reduced BP or associated symptoms of end-organ dysfunction (eg, hypotonia [collapse], syncope, incontinence)
2. Two or more of the following that occur rapidly after exposure to a likely allergen for that study participant (minutes to several hours):
    - Involvement of the skin-mucosal tissue (eg, generalized hives, itch-flush, swollen lips-tongue-uvula)
    - Respiratory compromise (eg, dyspnea, wheeze-bronchospasm, stridor, reduced peak expiratory flow, hypoxemia)
    - Reduced BP or associated symptoms (eg, hypotonia [collapse], syncope, incontinence)
    - Persistent gastrointestinal symptoms (eg, crampy abdominal pain, vomiting)
  3. Reduced BP after exposure to known allergen for that study participant (minutes to several hours): systolic BP of less than 90mmHg or greater than 30% decrease from that person's Baseline.

**PUBLIC COPY**  
This document cannot be used to support any marketing authorization application and any extensions or variations thereof.

BLQ	below the limit of quantification
BMI	body mass index
BP	blood pressure
C _{max}	maximum plasma concentration
COVID-19	coronavirus disease-19
CI	confidence interval
CRO	contract research organization
CSR	clinical study report
CV	coefficient of variation
DEM	data evaluation meeting
ECG	electrocardiogram
eCRF	electronic case report form
EudraCT	European Union Drug Regulating Authorities Clinical Trials
ES	Enrolled Set
FDA	US Food and Drug Administration
GLSM	geometric least square mean
GLSMR	geometric least square mean ratio

List of Abbreviations

HLT	high level term
ICF	informed consent form
ICH	International Council for Harmonisation
IgG	immunoglobulin G
IMP	investigational medicinal product
IPD	important protocol deviation
ISRQ	injection site reaction questionnaire
LLOQ	lower limit of quantification
LSM	least square mean
MedDRA	Medical Dictionary for Regulatory Activities
MP	manual push
MRD	minimum required dilution
MSR	minimum significant ratio
PCR	polymerase chain reaction
PCS	potentially clinically significant
PD	pharmacodynamic
PD-PPS	Pharmacodynamic Per Protocol Set
PDILI	potential drug-induced liver injury
PK	pharmacokinetic
PK-PPS	Pharmacokinetic Per Protocol Set
PT	preferred term
QTcF	QT corrected for heart rate using Fridericia's formula
R _{min}	maximum decrease in total plasma IgG
RS	Randomized Set
SAE	serious adverse events
SAP	Statistical Analysis Plan
SARS-CoV-2	severe acute respiratory syndrome coronavirus 2
SC	subcutaneous(ly)
SD	standard deviation

List of Abbreviations

SFU	Safety Follow-up
SIAQ	self-injection assessment questionnaire
SMC	safety monitoring committee
SOC	system organ class
SS	Safety Analysis Set
TEAE	treatment-emergent adverse event
TEMA	treatment-emergent markedly abnormal
TFLs	tables, figures, and listings
t_{\max}	time to maximum plasma concentration
t_{\min}	time to maximum plasma concentration
ULN	upper limit of normal
VAS	visual analog scale
WHODD	World Health Organization Drug Dictionary

1 INTRODUCTION

The purpose of this statistical analysis plan (SAP) is to provide all information that is necessary to perform the required statistical analysis of study UP0106. It also defines the summary tables figures, and listings (TFLs) to be included in the final clinical study report (CSR) according to the protocol.

This SAP is based on, and assumes familiarity, with the following documents:

- Protocol version- amendment 2, dated 03 June 2021.
- electronic Case Report Form (eCRF) version 3.0, dated 26 May 2021.

Unless specified in the sections below, the study will be analyzed as described in the most recent version of the protocol.

If a future protocol amendment necessitates a substantial change to the statistical analysis of the study data, this SAP will be updated accordingly. If, after database lock, additional analyses are required to supplement the planned analyses described in this SAP, those unplanned analyses will be described in a separate analysis plan. However, if analysis definitions have to be modified or updated prior to database lock, a further SAP amendment will be required.

The content of this SAP is compatible with the International Council for Harmonisation (ICH)/US Food and Drug Administration (FDA) E9 Guidance documents.

UCB is the Sponsor and ICON is the Contract Research Organization (CRO) for this study.

1.1 Objectives and Estimands/Endpoints

The study objectives and endpoints are presented in [Table 1-1](#).

Table 1-1: Study objectives and endpoints

Objectives	Endpoints/Estimands
Primary	

 To evaluate the safety and tolerability of a █████ SC dose of rozanolixizumab administered to healthy participants by manual push (MP) vs syringe driver 	
 Incidence of TEAEs
Secondary	

 To assess the PK and PD of a █████ SC dose of rozanolixizumab administered by MP vs syringe driver 	
 PK endpoints: 
 C_{max}, t_{max}, $AUC_{(0-t)}$ PD endpoints: 
 Baseline-corrected area under the Total IgG-time curve R_{min} t_{min}
Exploratory	

 To compare the PK and PD of a █████ SC dose of rozanolixizumab administered by MP vs syringe driver 	
 PK comparisons: C_{max}, $AUC_{(0-t)}$ PD comparison: Baseline-corrected Total IgG AUC

 To evaluate the immunogenicity of rozanolixizumab following SC administration 	
 Anti-rozanolixizumab antibody screening status (positive or negative screen), confirmatory status (positive or negative immunodepletion), and the titer for “positive immunodepletion” samples at each scheduled assessment during the In-Clinic and SFU Periods

 To evaluate the effects of rozanolixizumab on the concentrations of IgG on tetanus, influenza A virus-specific IgG antibody, and COVID-19 vaccinated/previously infected participants 	
 Values and change from Baseline in serum IgG concentrations at each scheduled assessment during the In-Clinic and SFU Periods Values and change from Baseline in tetanus, influenza A virus-specific IgG antibodies, and COVID-19 vaccinated/previously infected

Table 1-1: Study objectives and endpoints

Objectives	Endpoints/Estimands
	participants during the In-Clinic and SFU Periods

 To assess total volume, total time, and infusion rate for MP and syringe driver 	
 Volume of IMP administration Time from start to completion and resultant infusion rate of IMP administration Time of infusion setup for both modes of administration

 To assess acceptability of SC rozanolixizumab administration by MP vs syringe driver 	
 Post-dose infusion site pain visual analog scale with IMP administration

 To assess the experience with SC infusions 	
 Pre- and post-dose SIAQ for MP administration Post-dose ISRQ for syringe driver administration
Other Safety	

 To evaluate changes from Baseline in vital signs, 12-lead electrocardiogram, and laboratory measurements following █████ doses of rozanolixizumab administered by SC MP vs syringe driver in healthy study participants 	
 Vital signs measurements (blood pressure, pulse rate, respiratory rate, and body temperature), 12-lead electrocardiogram, and local tolerability assessments at each scheduled assessment during the In-Clinic and SFU Periods Changes from Baseline in clinical laboratory assessments will consist of hematology including coagulation, clinical chemistry, and urinalysis at each scheduled assessment during the In-Clinic and SFU Periods

 To further evaluate the safety and tolerability of a █████ SC dose of rozanolixizumab administered to healthy participants by MP vs syringe driver 	
 Occurrence of serious TEAEs Occurrence of treatment-related TEAEs Occurrence of TEAEs leading to withdrawal Occurrence of AEs of special monitoring Comparison of TEAEs for MP vs syringe driver Serum complement (C3, C4), and cytokines and plasma complement (C3a, C5a)

AE=adverse event; AUC=area under the concentration-time curve; $AUC_{(0-t)}$ =area under the concentration-time curve from 0 to time t; C_{max} =maximum plasma concentration; COVID-19=coronavirus disease-19; IgG=immunoglobulin G; IMP=investigational medicinal product; MP>manual push; ISRQ=injection site reaction questionnaire; PD=pharmacodynamic(s); PK=pharmacokinetic(s); R_{min} =maximum decrease in total plasma IgG; SC=subcutaneous(ly); SFU=Safety Follow-Up; SIAQ=self-injection assessment questionnaire;

TEAE=treatment-emergent adverse event; t_{max} =time to maximum plasma concentration; t_{min} =time to minimum IgG level.

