### 4.3 Justification for dose

The planned dose of rozanolixizumab for this study is [REDACTED], consistent with the primary recommended rozanolixizumab dose of [REDACTED] SC in future clinical dosing of rozanolixizumab in MG and ITP. Simulations from a population PK/PD analysis of clinical rozanolixizumab data demonstrated comparable systemic rozanolixizumab exposure and IgG response for a [REDACTED] fixed dose and [REDACTED] and [REDACTED] doses (both these latter doses being clinically effective in Phase 2 studies) for adults weighing  $\geq 35$ kg. The dose of [REDACTED] is identical to a weight-tiered dose of [REDACTED] for participants weighing  $\geq 70$ kg, a weight-tiered dose of [REDACTED] for participants weighing 50kg to <70kg, and a weight-tiered dose of [REDACTED] for participants weighing 35kg to <50kg. A [REDACTED] dose is also being assessed in low body weight participants to support future rozanolixizumab pediatric development programs.

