### 9.4.3 PD analyses

Total IgG (observed values, change from Baseline, and percentage change from Baseline) will be listed and summarized for the PD Per Protocol Set. The geometric mean Total IgG concentration with 95% confidence interval will be displayed graphically.

Derived parameters for the Total IgG response curve (AUC, maximum decrease in total plasma IgG, and time to minimum plasma concentration) will be listed and summarized for the PD Per Protocol Set.

The comparability of the total IgG Baseline-corrected  $AUC(IgG)/D$  between MP and the syringe driver will be assessed within an analysis of covariance model analogous to the analysis of variance model used to evaluate the PK parameters described above. The Baseline IgG value will be fitted as a covariate.

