2 STATISTICAL HYPOTHESES

Not applicable, there is no hypothesis testing in the study.

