5 STATISTICAL ANALYSES

5.1 General Considerations

This is a Phase 1 study to evaluate the safety and tolerability of a [REDACTED] SC dose of rozanolixizumab administered to healthy participants by MP vs syringe driver.

Statistical evaluation will be performed by UCB or designee with oversight by the Statistical Sciences and Innovation Department of UCB. All analyses will be performed using SAS[®] version 9.4 or later (SAS Institute, Cary, NC, USA).

Missing data will not be imputed. Outlier detection and statistical analysis of outliers will not be performed. Unless otherwise stated, Baseline will be the last non-missing data collected prior to the IMP administration ([refer Section 5.1.1.1.4](#)).

Continuous variables will be summarized by cohort and in each cohort by treatment groups rozanolixizumab [REDACTED] or placebo, and day (where applicable); with statistics including, the number of study participants, mean, standard deviation (SD), interquartile range, median, minimum, maximum, and 95% confidence interval (CI), if applicable. Categorical variables will be summarized by cohort, treatment group, and day (where applicable) with frequency counts and percentages. Coefficient of variation (CV) and geometric mean will be used for PK parameters.

In addition, the results will be summarized by administration method (manual push or syringe driver), and within administration method, by treatment group (rozanolixizumab, regardless of dose, or placebo).

When reporting relative frequencies or other percentage values, the following rules apply:

- For values where all participants fulfill certain criteria, the percentage value will be displayed as 100
- For values where the absolute frequency is zero, there will be no percentage displayed at all
- All other percentage displays will use 1 decimal place

-
- Percentages displayed based on continuous data (eg, percentage changes from Baseline) will be displayed to 1 decimal place eg, 100.0 and 0.0.
 - Unless otherwise stated, the percentages will be based on the number of participants in the respective analysis population and treatment group.

When reporting descriptive statistics, the following rules will apply in general:

- “n” will be an integer.
- Mean (arithmetic and geometric), 95% CI, SD, and median will use 1 additional decimal place compared to the original data.
- Coefficient of variance (CV [%]) will be presented with 1 decimal place.

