The geometric least square mean (GLSM), GLSM differences and the corresponding 90% CI for the differences (MP [Test] - syringe driver [Reference]) will be calculated for PK parameters (log-transformed C_{max} , AUC_{0-t}). Back-transformed (anti-log) estimates of (GLSM, geometric least square mean ratio (GLSMR) and its 90% CI for the comparisons will be presented. In order to verify the normality assumption of the ANOVA, normal quantile-quantile plots will be used to visually inspect the distribution of residuals, and the potential impact of any deviations will be discussed.

PD analyses

All PD summaries will be done using PD-PPS by treatment group described under [section 5.1.1.3](#). Total IgG (observed values, change from Baseline, and percentage change from Baseline) will be listed and summarized for the PD Per Protocol Set. The geometric mean Total IgG concentration with 95% CI will be displayed graphically.

Derived parameters for the Total IgG response curve (AUC, maximum decrease in total plasma IgG, and time to minimum plasma concentration) will be listed and summarized for the PD Per Protocol Set.

The comparability of the total dose adjusted IgG Baseline-corrected AUC (IgG)/D between MP and the syringe driver will be assessed within an ANCOVA model with Baseline IgG value fitted as a covariate. The least square mean (LSM), LSM differences and the corresponding 95% CI for

the differences will be presented for total IgG. The analysis may be conducted on the log scale if the data exhibits substantial non-normality. In this case, the reason for the log-transformation will be described.

The following contrasts will be presented:

- Rozanolixizumab via Syringe Driver vs Rozanoliximab via MP
- Placebo via Syringe Driver vs Placebo via MP
- Rozanolixizumab via Syringe Driver vs Placebo via Syringe Driver
- Rozanoliximab via MP vs Placebo via MP

Additionally, observed values and change from Baseline in serum IgG concentrations at each scheduled assessment during the In-Clinic and SFU Periods will be summarized descriptively.

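### The only modelled PD comparison of manual push with syringe driver divides IgG AUC by dose, with no case made for proportionality, although one manual push cohort appears to receive a different dose

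*SAP*

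**What the plan says.** The endpoint tables (SAP Table 1-1, protocol Table 3-1) name one PD comparison of the two methods: "PD comparison: Baseline-corrected Total IgG AUC". It is not divided by dose.

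The analysis text uses a different variable. SAP 5.4.1.2 assesses the "total dose adjusted IgG Baseline-corrected AUC (IgG)/D between MP and the syringe driver" in an ANCOVA. Protocol 9.4.3 also divides by D, builds the model by analogy with the PK analysis of variance (method as main effect), and adds: "The Baseline IgG value will be fitted as a covariate". Neither text has a dose, weight or cohort term. The output is least square mean differences with 95% CIs for four contrasts, three of which involve placebo.

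On dose, protocol 4.3 says that a further (redacted) "dose is also being assessed in low body weight participants to support future rozanolixizumab pediatric development programs". SAP 5.1 pools within method "by treatment group (rozanolixizumab, regardless of dose, or placebo".

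On inference, SAP section 2 states: "Not applicable, there is no hypothesis testing in the study".

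**The concern.** Dividing an outcome by dose is an adjustment with a built-in assumption: double the dose, double the response. If that fails and the doses are unevenly spread over the two methods, the method contrast absorbs part of the dose effect.

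That spread appears uneven here. The study is a preliminary look at MP before the technique is recommended (protocol 4.1), so a dose-scaling artefact could be read as a PD effect of delivery method. The endpoint table and the analysis text also disagree within each document. The SAP's list of changes to protocol-planned analyses (6.2) does not resolve this, since the protocol carries the same mismatch.

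**Working it through.** The plan gives no effect size, SD or power to reproduce. The counts agree: 4 × (6 + 2) = 32 in total and 4 × 6 = 24 active, so 12 MP (Cohorts 2 and 4) versus 12 syringe driver (Cohorts 1 and 3).

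**Is dose tied to method?** Four pieces of text, read together:
- Protocol 1.1 and 4.3 add a second dose, in low-weight participants only.
- Protocol 4.1 ties the fixed dose in that weight band to the syringe driver and a separate volume to MP. SAP 1.2 links that volume to a dose.
- SAP 5.1 pools active participants regardless of dose.
- SAP 5.4.1.2 omits covariates from the PK model because weight is balanced across methods. It says nothing about dose balance.

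The natural reading is that Cohort 2 alone has the second dose. The values are redacted, so this remains an inference.

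**Effect of the division.** Let r be the Cohort 2 dose relative to the common dose and e the ED50 relative to the common dose. Assume no method effect and R(D) = D/(e + D). Both r and e are assumptions.
- Cohort 2 response per unit dose, relative to the other cohorts: (1 + e)/(r + e)
- Pooled MP/syringe driver ratio on AUC/D: ½[1 + (1 + e)/(r + e)]
- The same ratio on undivided AUC: ½[1 + r(1 + e)/(r + e)]

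Example, r = 0.5 and e = 0.5: 1.5/1.0 = 1.5, so AUC/D gives ½(1 + 1.5) = 1.25 and undivided AUC gives ½(1 + 0.75) = 0.875.

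| r | e | AUC/D ratio | Undivided ratio | 95% CI on AUC/D excludes zero (CV 20/30/40%) |
|---|---|---|---|---|
| 0.5 | 0.1 | 1.42 | 0.96 | 73/49/33% |
| 0.5 | 0.5 | 1.25 | 0.875 | 46/28/18% |
| 0.5 | 1 | 1.17 | 0.83 | 29/16/12% |
| 0.75 | 0.1 | 1.15 | 0.985 | 24/15/11% |
| 0.75 | 1 | 1.07 | 0.93 | 11/7/6% |
| 0.9 | 0.1 | 1.05 | 0.995 | not simulated |
| 0.5 or 0.75 | proportional | 1.00 | 0.75 or 0.875 | about 5% |

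The last column comes from 4,000 simulated ANCOVAs per setting (method plus Baseline IgG, 12 versus 12 active). Baseline was drawn from 7 to 16 g/L, the limits in exclusion criterion 38, and response was scaled to Baseline. The CVs are assumed.

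**Direction.** It depends on the curve. With R(D) = D²/(1 + D²), the Cohort 2 per-dose ratio is (0.2/0.5)/0.5 = 0.80 at r = 0.5 and (0.36/0.5)/0.75 = 0.96 at r = 0.75. The pooled ratios are ½(1 + 0.80) = 0.90 and ½(1 + 0.96) = 0.98, so MP now looks weaker. A Cohort 2 dose above the common one would also reverse the sign under the saturating curve.

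**Candidate repairs.**
- *Drop the division only.* The bias turns the other way (undivided column). At r = 0.5 the CI excluded zero in 6% to 61% of runs.
- *Undivided AUC plus a dose term.* The term is a Cohort 2 indicator, so the method contrast becomes Cohort 4 minus the mean of Cohorts 1 and 3, which differ in weight. If low-weight response at the same dose were 20% or 40% higher (assumed), the bias is 1 − (1.2 + 1)/2 = −0.10 or 1 − (1.4 + 1)/2 = −0.20. Simulated at CV 15%, the CI excluded zero in about 16% to 30% of runs.
- *Undivided AUC plus dose and weight terms.* The method contrast is effectively Cohort 3 versus Cohort 4. Bias stayed near zero and exclusions at or below about 6%. A direct Cohort 3 versus 4 fit gave 4% to 5% in the no-weight-effect settings.

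**The case against.** The SAP follows a variable that the protocol prespecified, in parallel with the dose-adjusted PK parameters. The comparison is exploratory and nothing is tested. Undivided IgG AUC, R_min and t_min are also summarised by cohort, so a reader can set Cohort 3 beside Cohort 4. If the two doses are close, the artefact is trivial. All of this stands, and it limits the consequence. It does not supply a reason for assuming proportionality in the one modelled comparison.

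A reader might go further and infer that IgG lowering is known to be non-proportional and that MP will therefore look stronger per mg. The documents do not support that:
- IgG cannot fall below zero, but a ceiling does not show curvature between two redacted doses. Protocol 2.2 calls the fall dose-dependent and mentions no plateau. It also says vaccine-specific IgG tracked total IgG, lowest around Day 10 and near Baseline by Day 57, so the area over follow-up is well short of its cap.
- Protocol 4.3 may look like evidence of saturation, because simulated IgG response was comparable across a fixed dose and two others. The same sentence says exposure was comparable too, so it equates dosing schemes.
- Protocol 2.2 reports no detectable drug at one SC dose and detection in only two participants at another. This suggests non-linear exposure, but it could equally fit a threshold-type curve, which can push the artefact the other way.

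**Conclusion.** The point holds as an unjustified analysis choice and an endpoint mismatch. The modelled variable is AUC(IgG)/D, the listed endpoint is undivided AUC, and proportionality is assumed without argument while dose is, very probably, partly confounded with method.

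Size and direction cannot be established from the documents. Under the assumed saturating curve the spurious MP/syringe driver ratio runs from 1.05 or less (r = 0.9, e of 0.1 or more) to 1.42 (r = 0.5, e = 0.1). It is 1.00 under exact proportionality and below 1 under some other curves. These figures rest on assumed dose ratios, curves and CVs, and on the inference that only Cohort 2 has the second dose.

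The harm is a misleading exploratory estimate and CI, not a failed test. Separately, protocol Table 6-1 gives placebo no dose level, so AUC/D has no defined value in the three contrasts that involve placebo. SAP 5.4.1.2 needs repair on that ground alone. No view is taken on which dose is right.

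**What to change.** In SAP 5.4.1.2, analyse undivided Baseline-corrected AUC(IgG), as Table 1-1 lists it. For the active MP versus syringe driver contrast, fit method, Baseline IgG, dose level and weight category. This is in effect the Cohort 3 versus Cohort 4 comparison: those cohorts are randomised between methods and presumed to share a dose, whereas low-weight participants are assigned to a method by order of recruitment. Report AUC(IgG)/D descriptively, for active arms only. Undivided AUC also makes the placebo contrasts computable. Align protocol 9.4.3 with this, or record the departure in SAP 6.2.

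The cost is SAP wording and two model terms, with no new data or participants. The downside should be stated in the plan: Cohort 2 then adds almost nothing to the method contrast, which rests on about 6 versus 6 active participants. For the same residual SD σ, the standard error rises from σ√(1/12 + 1/12) = 0.41σ to σ√(1/6 + 1/6) = 0.58σ, a factor of √2 ≈ 1.41. Fitting all 24 active participants leaves 24 − 5 = 19 residual degrees of freedom, against 12 − 3 = 9 if Cohorts 3 and 4 are analysed alone, so the four-cohort model is the better way to take the contrast.
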